## **8.0 STUDY PLAN**

### **8.1 Study Procedures**

The following sections describe the study procedures and data to be collected. For each procedure, subjects are to be assessed by the same investigator or site personnel whenever possible. The Schedule of Study Procedures is located in Appendix A.

#### **8.1.1 Informed Consent Procedure**

Informed consent must be obtained prior to the subject entering into the study and before any protocol-directed procedures are performed.

A unique subject identification number (subject number) will be assigned to each study subject at the time that the study subject signs the informed consent. This subject number will be used throughout the study.

#### **8.1.2 Demographics, Medical History, and Medication History Procedure**

Demographic information to be obtained will include date of birth, sex, ethnicity, race as described by the subject, and smoking status of the subject at Screening.

Medical history to be obtained will include determining whether the subject has any significant conditions or diseases relevant to the diagnosis of SAR/PAR (i.e., diseases under study) that stopped at or prior to signing of informed consent. Ongoing conditions are considered concurrent medical conditions (see Section 8.1.8).

#### **8.1.3 Physical Examination Procedure**

A baseline physical examination (defined as the assessment prior to first dose of investigational immunotherapy) will consist of the following body systems: (1) eyes; (2) ears, nose, throat; (3) cardiovascular system; (4) respiratory system; (5) gastrointestinal system; (6) dermatologic system; (7) extremities; (8) musculoskeletal system; (9) nervous system; (10) lymph nodes; (11) other. All subsequent physical examinations should assess clinically significant changes from the assessment prior to first immunotherapy examination.

#### **8.1.4 Weight, Height**

A subject should have weight and height measured while wearing indoor clothing and with shoes off.

#### **8.1.5 Vital Sign Procedure**

Vital signs will include body temperature, respiratory rate, blood pressure (resting more than 5 minutes), pulse (bpm), and peaked flow (PFR).

When vital signs are scheduled at the same time as blood draws, the blood draw will take priority and vital signs will be obtained within 0.5 hour before or after the scheduled blood draw.

#### 8.1.6 Primary Efficacy Measurement

The primary efficacy measurement is based upon validated efficacy instruments. Details of the efficacy assessments are described in Appendix F

#### 8.1.7 Documentation of Concomitant Medications

Concomitant medication is any drug given in addition to the study immunotherapy. These may be prescribed by a physician or obtained by the subject over the counter. Concomitant medication is not provided by the study sponsor. At each study visit, subjects will be asked whether they have taken any medication other than the study medication (used from signing of informed consent through the end of the study), and all medication including vitamin supplements, over-the-counter medications, and oral herbal preparations, must be recorded in the CRF.

#### 8.1.8 Documentation of Concurrent Medical Conditions

Concurrent medical conditions are those significant ongoing conditions or diseases that are present at signing of informed consent. The investigators will decide upon the significance or non-significance of an ongoing clinical condition or laboratory abnormality.

#### 8.1.9 Procedures for Clinical Laboratory Samples

All samples will be collected in accordance with acceptable laboratory procedures. Blood will be drawn at the start of the study and at the completion. The maximum volume of blood at any single visit is less than 10.0 mL, and the approximate total volume of blood for the study is less than 20 mL. Serum collected at the screening visit will be stored for later analysis. Blood will be redrawn at the final visit (week 14) so that pre and post immunoglobulin levels can be measured including specific IgE, and IgG4 and possibly IgG3.

The Johns Hopkins Bayview Medical Center laboratory will perform laboratory tests as indicated above. The investigator or designee is responsible for transcribing or attaching laboratory results to the CRF. The investigator will maintain a copy of the laboratory accreditation and the reference ranges for the laboratory used.

#### 8.1.10 Pregnancy

If any subject is found to be pregnant during the study she should be withdrawn and immunotherapy should be immediately discontinued. If the pregnancy occurs during administration of active PMA study immunotherapy the pregnancy should be reported immediately, using a pregnancy notification form, to the contact listed in Section 1.0.

Should the pregnancy occur during or after administration of immunotherapy, identified as being PMA, the investigator must inform the subject of their right to receive treatment information. Subjects randomized to placebo do not need follow-up.

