The labeling of study PMA and placebo solutions will be undertaken by the compounding pharmacy of this investigation and undertaken in conjunction with the sponsor so that a double-blind study technique can be employed during the investigation. Each active and placebo vial set will be labeled randomly either set I or II. The set, mix letter, dilution, and use by date will also be included as shown by the example below. Only the pharmacy and sponsor will hold the treatment set randomization code. Recruited subjects will alternate between sets I and II.

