### **7.3 Unblinding Procedure**

The investigational drug blind shall not be broken by the investigator unless information concerning the investigational immunotherapy is necessary for the medical treatment of the subject. In the event of a medical emergency, if possible, the medical monitor should be contacted before the investigational immunotherapy blind is broken to discuss the need for unblinding.

For unblinding a subject, the investigational immunotherapy blind can be obtained by contacting the vendor compounding pharmacist. The sponsor must be notified as soon as possible if the investigational immunotherapy blind is broken. The date, time, and reason the blind is broken must be recorded in the study subject's source documents and the same information must be recorded on the subject's CRF. Investigational immunotherapy must be stopped immediately and the subject must be withdrawn from the study.

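### Section 8.1.10 ties pregnancy notification, the duty to inform and follow-up to an arm the blinded site does not know; separately, no schedule lists the pregnancy tests promised in Appendix C

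*Combined protocol and SAP*

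**What the plan says.** Section 8.1.10 begins without regard to arm: any subject found pregnant is withdrawn and dosing stops. Three further actions then depend on treatment.

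- Notification: "If the pregnancy occurs during administration of active PMA study immunotherapy the pregnancy should be reported immediately", on a pregnancy notification form.
- Duty to inform: for a pregnancy during or after immunotherapy "identified as being PMA, the investigator must inform the subject of their right to receive treatment information".
- Follow-up: "Subjects randomized to placebo do not need follow-up".

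On who knows the arm, 7.1.1 states: "Only the pharmacy and sponsor will hold the treatment set randomization code". Section 7.3 says that the blind "shall not be broken by the investigator unless information concerning the investigational immunotherapy is necessary for the medical treatment of the subject". It gives a route to the code, since "the investigational immunotherapy blind can be obtained by contacting the vendor compounding pharmacist", and it requires documentation and withdrawal once the blind is broken. Pregnancy is not mentioned there.

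Appendix C item 24 lists what the consent must cover. It has no arm condition: if a subject is found pregnant, immunotherapy stops and the investigator offers her the choice of learning her treatment. The same item promises repeated pregnancy testing of women of childbearing potential during the study. Section 8.3 refers to Appendix A as the schedule for all study-related procedures.

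**The concern.** The three conditional actions fall to a site that is meant not to know which condition applies. A rule of that kind puts pressure on the blind, or is applied unevenly, or both. It also waives follow-up for placebo subjects although every pregnant subject has been in the same trial. Placebo is not an empty exposure here: the vials contain histamine, folic acid, glycerin and phenol (7.1.1 and 7.1.3.2), and both arms share a rescue ladder that reaches oral prednisone (Appendix I). If only PMA pregnancies are followed, an adverse outcome on PMA has no concurrent comparator.

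The testing gap is separate. Non-pregnancy is an inclusion criterion (6.1 item 3), Section 6.0 wants entry criteria confirmed before the first dose, and withdrawal on pregnancy depends on detecting it. A coordinator working from the visit schedule would find no test to perform.

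**Working it through.** The plan gives no figure to reproduce. The check compares sections, counts schedule entries and sizes the event.

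**1. Can a blinded site apply 8.1.10?** Each conditional action needs the arm; the site does not hold it (7.1.1); 7.3 does not list pregnancy as a reason to obtain it. Three ways of acting remain.

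- Report and follow every pregnancy. This needs no code, but 8.1.10 does not instruct it.
- Ask the pharmacist for the assignment. This breaks the blind on a ground that 7.3 does not name, unless the information is needed for her medical care.
- Leave the sorting to a code holder. The site stays formally blind, but a request for follow-up, or its absence, signals the arm.

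**2. Does 8.1.10 contradict Appendix C item 24?** No. A site that offers treatment information to every pregnant subject satisfies both. The two differ in scope: 8.1.10 covers treatment identified as PMA; item 24 covers any pregnant subject.

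**3. What is captured in both arms already?**

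- Withdrawal (8.1.10) and pregnancy as a recorded withdrawal reason (6.4 item 6).
- SAE reporting, including congenital anomaly or birth defect (9.1.4 item 5) and fetal loss (Table 9.a).
- Follow-up of SAEs to resolution or permanent outcome (9.3).

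The limit is time. The study lasts about 14 weeks, so the term outcome of a pregnancy conceived on study falls after it. Once the AE collection period is over, 9.2.2 requires a report only if the SAE is spontaneously reported and considered related to participation.

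**4. How often would this arise?** Assumed, because the documents give neither figure: 9 to 18 women of childbearing potential among the 36 subjects, and 1% to 8% pregnancies per woman-year. Expected number = women × annual rate × weeks/52; chance of at least one = 1 − exp(−expected number).

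- 8 treatment weeks, the window of the notification clause: 9 × 0.01 × 8/52 = 0.014; 18 × 0.08 × 8/52 = 0.222. Chance of at least one: 1.4% to 19.9%.
- Placebo share at 1:1, same 8 weeks: 0.014/2 = 0.007; 0.222/2 = 0.111. Chance of at least one: 0.7% to 10.5%.
- From first dose to week 14 (weeks 3 to 14, 12 weeks), nearer the during-or-after window of the duty to inform: 9 × 0.01 × 12/52 = 0.021; 18 × 0.08 × 12/52 = 0.332. The two pre-dose washout weeks are left out because no clause on immunotherapy applies to them.

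Exclusion criterion 6 and the contraception requirement in Appendix C item 24 point to the lower part of these ranges.

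**5. Is a pregnancy test scheduled?** Appendix A: 0 of 18 procedure rows. Screening (8.3.1): 0 of 8 items. Final visit or early termination (8.3.4): 0 of 7 items. Sections 8.3.2, 8.3.3 and 8.3.5 and the laboratory section 8.1.9 name none. Appendix A does have an inclusion/exclusion row at visit 1, so eligibility is checked there; how pregnancy status is established is not stated.

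**The case against.** The strongest reply is that little depends on the wording. A pregnant subject is withdrawn and stops dosing in either arm, and 7.3 would withdraw her after unblinding anyway, so learning her arm touches at most her early-termination assessments. Serious outcomes are SAEs in both arms. The passive wording of the duty to inform can be read as identification by the code holder. The notification contact in Section 1.0 and the form itself are not available to this review and may settle who does the sorting. Appendix C is part of a protocol the investigator has agreed to follow (Appendix B item 1), and the consent form, also unavailable, may name the test visits. The event is rare.

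Most of this stands and limits the size of the point. It does not remove it: 8.1.10 still gives the site instructions it cannot carry out without the code, still exempts one arm from follow-up, and the protocol's own schedule still omits a procedure that Appendix C commits to.

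A reader might infer more than the documents support:

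- That placebo pregnancies go unrecorded. They do not (6.4 item 6 and the SAE rules).
- That follow-up to delivery is waived for placebo but guaranteed for PMA. Section 8.1.10 does not define follow-up for either arm.
- That pregnancy status is not checked before dosing, or that no testing is intended. The visit 1 eligibility row and Appendix C say otherwise; what is missing is a named, scheduled test.
- That one unblinding for pregnancy would expose every subject's arm, and that this should count here. That exposure comes from the two-label scheme ("Each active and placebo vial set will be labeled randomly either set I or II"), a separate matter.

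**Conclusion.** The point holds in limited form. Section 8.1.10 makes notification, the duty to inform and follow-up depend on an assignment the site does not have, and it is narrower than Appendix C item 24. Separately, the promised pregnancy tests appear in no visit schedule. Both conclusions come from the text and need no assumption.

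The size rests on the assumed 9 to 18 women and 1% to 8% per year: most likely no pregnancy occurs, and at the upper end there is about a one-in-five chance of at least one during treatment. The testing gap is not rare in the same sense, since it concerns every woman of childbearing potential enrolled. No bias in a planned efficacy or safety comparison is shown. Severity is minor to should-fix: the effect on the analysis is negligible, but the defect concerns subject protection and the blind and is cheap to remove.

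**What to change.** - **8.1.10:** require the same immediate notification and the same follow-up for every pregnancy, whatever the arm and without unblinding the site. State how long follow-up lasts. Delete the sentence "Subjects randomized to placebo do not need follow-up".
- **Offer of treatment information:** extend it to any pregnant subject, made by the investigator as in Appendix C item 24.
- **7.3:** name this case. The existing record stays ("The date, time, and reason the blind is broken must be recorded in the study" subject's source documents and on the CRF). Where feasible, disclose the code to the subject without the arm being recorded at the site.
- **Appendix A and 8.3:** add a pregnancy-test row for women of childbearing potential, at least before the first dose and at visit 18 or Early Termination. Word the first test relative to the first dose, because 8.3.2 places that dose at visit 1 and Appendix H at visit 2.

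Cost: amendment wording and one schedule row. Two test points for 9 to 18 women (assumed) come to 2 × 9 = 18 to 2 × 18 = 36 tests, and each further test visit adds 9 to 18; Appendix C already commits to testing of this kind. There would be a few more forms and contacts for placebo subjects, possibly beyond week 14, and the consent would have to cover that later contact. A subject who learns her arm could still tell site staff; the wording cannot prevent that.

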#### 8.1.11 Documentation of Screen Failure

Investigators must account for all subjects who sign an informed consent. If screening factors dictate that the subject is not eligible to continue in the investigation, the investigator should complete the CRF.

The primary reason for screen failure is recorded in the CRF using the following categories:

- PTE/AE.
- Did not meet inclusion criteria or did meet exclusion criteria.
- Significant protocol deviation.
- Lost to follow-up.
- Voluntary withdrawal.
- Study termination.
- Other

Subject numbers assigned to subjects who fail screening should not be reused.

#### 8.1.12 Documentation of Study Randomization

Only subjects who meet all of the inclusion criteria and none of the exclusion criteria are eligible for randomization into the immunotherapy treatment phase.

#### 8.1.13 Allergen Skin Prick Testing Procedures

All subjects will undergo allergen skin prick allergy testing (SPT) as per standard of care using the Multi-Test PC (Lincoln Diagnostics, Decator, IL) or comparable skin testing device. The results of the skin testing will dictate if subjects qualify for the study. In addition to having clinical symptoms of perennial allergic rhinitis, all subjects test positive to at least 6 of 48 total SPT including at least one dust mite species (D. farinae or D. pteronissinus). A positive skin test will be defined as a minimum wheal diameter of 5mm and at least 2mm greater than the saline control. A list of allergens used for testing is shown in Appendix H.

### **8.2 Monitoring Subject Treatment Compliance**

Study subject compliance will be monitored by the accuracy of their attendance at the study site for their bi-weekly immunotherapy treatments. If a subject is persistently noncompliant with the follow up clinic visits for immunotherapy, it may be appropriate to withdraw the subject from the

study. All subjects should be re instructed about the essentiality of scheduled clinic follow-up visits for immunotherapy during each of their scheduled clinic visits.

### **8.3 Schedule of Observations and Procedures**

The schedule for all study-related procedures for all evaluations is shown in Appendix A. Assessments should be completed at the designated visit/time point(s).

#### **8.3.1 Screening**

Subjects will be screened prior to the 14 day medication washout period. Subjects will be screened in accordance with predefined inclusion and exclusion criteria as described in Section 6.0. See Section 8.1.11 for procedures for documenting screening failures.

Procedures to be completed at Screening (Visit 1) include:

- Informed consent.
- Demographics, medical history, and medication history.
- Physical examination.
- Vital signs.
- Weight, height
- Concomitant medications.
- Concurrent medical conditions.
- Allergy skin prick skin testing.

#### **8.3.2 Study Entrance Randomization**

Study Randomization will take place on study day 1 (Visit 1). The following procedures will be performed and documented during Study Randomization:

- If the subject has satisfied all of the inclusion criteria and none of the exclusion criteria for randomization and the investigator deems the laboratory screening and skin testing are acceptable for continuance in the investigation, the subject should be randomized using the randomization sequence provided by the sponsor.
- Subjects will receive their first sub-cutaneous administration of immunotherapy with dose vial #5.
- The procedure for documenting Screening failures is provided in Section 8.1.11.

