## **5.0 STUDY DESIGN AND METHODS**

### **5.1 Study Design**

This is a phase 2 proof of concept study. It is being undertaken to characterize and quantify the clinical difference in signs and symptoms that may evolve when subjects with active SAR/PAR are administered a sub-cutaneous form of immunotherapy in a double-blind, prospective, controlled six weeks study wherein a PMA is compared with saline placebo.

Randomization to active PMA versus placebo treatment is on a 1 to 1 ratio. A double-blind study design is used to minimize outcome bias. Randomization measures to minimize bias at study entry include computerized random assignment of treatment versus placebo vials.

Subjects who are receiving nasal steroids for their SAR/PAR at screening may continue in the screening process if they agree to discontinue their therapy and commence a 14 day wash-out period of their medication prior to receiving active/placebo immunotherapy. Potential study subjects who, at screening, are not on active treatment for their SAR/PAR and asthma may enter directly into the investigation provided they fulfil entry and exclusion criteria and screening testing requirements.

The population to be studied consists of male and female adults aged 18 years to 65 years who are actively manifesting SAR/PAR have a score of at least 28 on the mini-RQLQ and 6 on the TNSS scale.

[figure not shown]
The active treatment phase of the study will be for six weeks with a safety followup assessment at 30 days post-treatment. No interim analysis is planned.

The study immunotherapy that will be evaluated in this study is a new innovative proprietary mixture of FDA approved allergens which has been clinically developed and evaluated, during the past three decades, in some 20,000 patients by the inventor of the mixture (see 3.2). In clinical evaluation this patented antigen mixture has provided clinical symptomatic relief to patients with SAR/PAR in as brief a period as three administrations of immunotherapy injections and has an observed overall success rate of approximately 80 to 90 percent of such treated subjects.

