### 8.3.3 Treatment Phase

Study visits 1 through 12 will be conducted (Figure 6a) in the study clinic and at each of these visits the study subject will have a safety and efficacy assessment and if deemed appropriate by the investigator will receive their next sub-cutaneous administration of study immunotherapy. A 60 minute post treatment in-clinic safety assessment will be conducted.

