### **14.2 Risks**

**Allergy Skin test** The risk of performing allergy skin testing is minimal. Serious reactions are rare. This study uses histamine and allergen for testing, which very rarely can cause serious reactions.

Most individuals experience mild to moderate itching at the site of testing that spontaneously resolves. You may feel some mild discomfort from the skin prick device itself.

**Immunotherapy** The most common side effect from allergen immunotherapy is slight swelling and discomfort at the site of the injection. This usually resolves in 1-2 days with the use of a cool pack. There is a very small chance of having a serious allergic reaction. If symptoms of a serious allergic reaction occur we would administer epinephrine and possibly other allergy medications such as antihistamines.

Some participants will receive placebo instead of active immunotherapy. These individuals may not see an improvement in their symptoms. All patients will be required to discontinue nasal steroids for two weeks prior to starting treatment. There is a risk that nasal symptoms could worsen when you stop the medication.

**Blood Draw** The most common side effect of blood draw is discomfort from the needle. This can sometimes lead to bruising of the skin. There is a very small chance of getting an infection from puncturing the skin.

**Other risks** There always exists the potential for loss of confidentiality; however, there are procedures in place to minimize this. Study information will not be associated with your private demographic information directly but linked via a numerical code only to be accessed by the study designers. However, there still remains the possibility that information about you may become known to people outside of this study.

You may get tired or bored when we are asking you questions or you are completing questionnaires. You do not have to answer any question you do not want to answer. There may be side effects and discomforts that are not yet known.

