## STUDY DESIGN AND METHODS

### Study Design

This is a phase 2 proof of concept study. It is being undertaken to characterize and quantify the clinical difference in signs and symptoms that may evolve when subjects with active seasonal or perennial allergic rhinitis (SAR/PAR) are administered a sub-cutaneous form of immunotherapy in a double-blind, prospective, controlled six weeks study wherein a proprietary mixture of FDA approved allergens (PMA) is compared with saline placebo.

Randomization to active PMA versus placebo treatment is on a 1 to 1 ratio. A double-blind study design is used to minimize outcome bias. Randomization measures to minimize bias at study entry include computerized random assignment of treatment versus placebo vials.

Subjects who are receiving nasal steroids for their SAR/PAR at screening may continue in the screening process if they agree to discontinue their therapy and commence a 14-day wash-out period of their medication prior to receiving active/placebo immunotherapy. Potential study subjects who, at screening, are not on active treatment for their SAR/PAR and asthma may enter directly into the investigation provided they fulfil entry and exclusion criteria and screening testing requirements.

The population to be studied consists of male and female adults aged 18 years to 65 years who are actively manifesting SAR/PAR have a score of at least 28 on the mini-RQLQ and 6 on the TNSS scale.

[figure not shown]
The active treatment phase of the study will be for six weeks with a safety follow-up assessment at 30 days post-treatment. No interim analysis is planned.

The study immunotherapy that will be evaluated in this study is a new innovative proprietary mixture of FDA approved allergens which has been clinically developed and evaluated, during the past three decades, in some 20,000 patients by the inventor of the mixture (see 3.2). In clinical evaluation this patented antigen mixture has provided clinical symptomatic relief to patients with SAR/PAR in as brief a period as three administrations of immunotherapy injections and has an observed overall success rate of approximately 80 to 90 percent of such treated subjects.

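### Sections 8.3.2 and 8.3.3 put randomisation and the first injection at the pre-washout screening visit and treatment at visits 1-12, against visit 2 and visits 2-17 in the rest of the plan

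*Combined protocol and SAP*

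**What the plan says.** Section 8.3.1 makes Visit 1 the screening visit and places it ahead of washout: "Subjects will be screened prior to the 14 day medication washout period". Section 8.3.2 then states: "Study Randomization will take place on study day 1 (Visit 1". Among the procedures for that session it lists the first subcutaneous injection, from vial #5. Section 8.3.3 continues: "Study visits 1 through 12 will be conducted (Figure 6a) in the study clinic", with an injection at each visit if the investigator deems it appropriate.

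The rest of the plan follows another calendar. The abstract (1.2) has the subject abstain from intranasal steroids and antihistamines for two weeks after screening and then return for the first injection. Section 9.2.1.1 ties first administration to visit 2. Appendix A runs screening (visit 1), washout, treatment (visits 2-17) and follow-up (visit 18). Appendix H lists injections from visit 2 to visit 17. The SAP takes its change scores from visit 2.

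Treatment duration is also given two ways. Section 5.1 says "The active treatment phase of the study will be for six weeks with a safety followup assessment at 30 days post-treatment", and the Study Design section of the SAP repeats it: "The active treatment phase of the study will be for six weeks with a safety follow-up assessment at 30 days post-treatment". Both sections also state eight weeks of treatment with twice-weekly visits.

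**The concern.** Sections 8.3.2 and 8.3.3 are the operative instructions for randomising and treating a subject, and they cannot be followed together with the schedule in the appendices. With the schematic not shown, 8.3.2 is also the only readable text that names the visit of randomisation; Appendix A has no row for it and marks inclusion/exclusion at visit 1 only.

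Three things would go wrong if 8.3.2 were applied as written:

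- Randomisation and the first dose would come before washout.
- Section 6.1, criterion 4, takes the RQLQ and TNSS scores at visits 1 and 2 and lets either day qualify. A subject who reaches both thresholds only at visit 2, off medication, could not be randomised at the stated visit, although criterion 4 admits that subject.
- The visit 2 value from which the SAP measures change would be taken after treatment had begun.

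If 8.3.3 were applied as written, dose escalation would end before the strongest vial in the schedule.

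**Working it through.** **1. The two calendars side by side**

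| Item | 8.3.1 to 8.3.3 | Elsewhere |
|---|---|---|
| Visit 1 | Screening, randomisation and first injection | Screening only (Appendix A) |
| Washout | After Visit 1, so after the first injection | Between visit 1 and visit 2 (Appendix A, abstract) |
| First injection | Visit 1 | Visit 2 (9.2.1.1, Appendix H) |
| Treatment visits | 1-12 | 2-17 (Appendices A and H) |
| Start of change scores | Not stated | Visit 2 (SAP) |

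**2. Visit counts**

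Inputs: eight weeks at two visits per week (5.1); visits 2-17 (Appendices A and H); final visit 18 (8.3.4).

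- Planned injections: 8 × 2 = 16, and 17 − 2 + 1 = 16. The plan's schedule reproduces.
- Total visits: 1 screening + 16 injection + 1 final = 18, matching 8.3.4. Section 14.3 pays 18 dollars a visit up to 325 dollars in total, and 18 × 18 = 324, which also fits 18 visits.
- Section 8.3.3: 12 visits ÷ 2 per week = 6 weeks. That fits the six-week wording in 5.1 and the SAP, and not the 16-injection schedule.

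**3. Allergen delivered if treatment stops as 8.3.3 implies**

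Inputs from Appendix H: each of vials #5, #4, #3 and #2 is used four times, at 0.05, 0.10, 0.15 and 0.20 ml per mix. Nominal dilutions are 1:625, 1:125, 1:25 and 1:5. Dose is volume × dilution, in ml of vial #1 per mix.

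- Volume per vial: 0.05 + 0.10 + 0.15 + 0.20 = 0.50 ml.
- All 16 injections: 0.50 × (1/625 + 1/125 + 1/25 + 1/5) = 0.50 × 0.2496 = 0.1248.
- First 12 injections (vials #5 to #3): 0.50 × (1/625 + 1/125 + 1/25) = 0.50 × 0.0496 = 0.0248.
- Ratio: 0.0248 / 0.1248 = 19.9%.
- Highest single dose: 0.20/25 = 0.008, against 0.20/5 = 0.040 planned, or 20%. Vial #2 is never reached.

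If dosing starts at visit 2 but stops at visit 12, only 11 injections are given: (0.0248 − 0.008) / 0.1248 = 0.0168 / 0.1248 = 13.5%.

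**4. Effect on the SAP's starting value**

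Six SAP comparisons start at visit 2: DCS to visits 17 and 18, mini-RQLQ to visits 17 and 18 (the four primary outcomes), and TNSS to visits 17 and 18 (secondary). Under literal 8.3.2 all six would start from a post-treatment value. Appendix A would still supply a mini-RQLQ and TNSS from visit 1. The DCS would have no pre-treatment value, because its first diary period is week 2 (12.1.3), after a Visit 1 injection.

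**The case against.** The strongest reply is that this is leftover visit numbering and that the surrounding text already corrects it. Section 8.3 says "The schedule for all study-related procedures for all evaluations is shown in Appendix A", and that appendix puts treatment at visits 2-17 after washout. Section 5.1 requires subjects on nasal steroids to "commence a 14 day wash-out period of their medication prior to receiving active/placebo immunotherapy". Section 14.2 is broader: "All patients will be required to discontinue nasal steroids for two weeks prior to starting treatment". Section 6.0 requires all entry criteria to be confirmed before the first dose, and 8.1.12 and 8.3.2 itself restrict randomisation to subjects who meet them. Appendix H has no visit 1 dose and fixes 16 injections. Because either day's scores qualify, a subject above both thresholds at visit 1 is already eligible on scores. Untreated subjects may enter directly under 5.1, so no washout is bypassed for them.

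Most of this stands. Dosing before washout, or stopping at 12 injections, would mean ignoring several explicit passages. What does not fall away is the contradiction itself. A site cannot obey both 8.3.2 and Appendix H, and no passage restates the randomisation visit correctly. The direct-entry clause also leaves one route by which a Visit 1 injection could seem permitted, and that would undermine the visit 2 starting value.

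A reader might go further and infer that subjects would be randomised at Visit 1, leave during washout undosed, and so drop out of the full analysis set despite the stated intent-to-treat approach. The documents do not support that. Section 8.3.2 describes randomisation and first injection as one session, so moving the injection to visit 2 moves randomisation with it. A gap between the two appears only if half of the mislabelled visit is corrected. Section 9.2.1.1 collects pretreatment events until first administration or screen failure, and 8.1.11 counts loss to follow-up and voluntary withdrawal among screen-failure reasons. Losses before visit 2 therefore look like screen failures. No washout-loss rate or shrinkage of the analysis set should be claimed.

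**Conclusion.** The inconsistency is real and should be corrected. As written, 8.3.2 and 8.3.3 are wrong operative rules. The first gives the wrong visit for randomisation and first dose; the second gives 12 treatment visits where the schedule has 16.

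The consequences are conditional on following those sections literally. The roughly 20% cumulative-dose figure assumes nominal dilutions and the Appendix H steps taken in order from the first treatment visit. The six affected SAP comparisons assume an injection at Visit 1. Neither outcome is likely given the other sections, and nothing here shows that subjects would in fact be dosed before washout. No sample size, alpha or power figure changes. The reason to act is that the randomisation visit decides which subjects can enter and whether the SAP's starting value is pre-treatment, and the plan states that visit incorrectly.

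**What to change.** - **8.3.2:** state that randomisation and the first injection both take place at visit 2, after washout, once the visit 2 scores are recorded and eligibility is confirmed.
- **8.3.3:** change the treatment visits to 2-17.
- **Appendix A:** add a randomisation row marked at visit 2, and extend the inclusion/exclusion row to visit 2.
- **5.1 and the Study Design section of the SAP:** change six weeks to eight weeks, twice in each.

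The cost is one sentence each in 8.3.2 and 8.3.3, two row edits and four short phrases. The visit schedule in Appendices A and H, the number of subjects and the statistical tests stay as they are.
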